Study Title: Comparison between angled-tip and straight-tip guidewire in biliary cannulation: A prospective, randomized trial
Protocol Version Number: Version 1.0 Protocol Date: 08/29/2022

Title Page:

Comparison between an angled-tip and straight-tip guidewire in biliary cannulation: a prospective, randomized trial

Principle Investigator:

[name] MD

Program Director, Advanced Endoscopy Fellowship

Director of Advanced Endoscopy

Clinical Associate Professor of Medicine, Tufts University School of Medicine

Division of Gastroenterology and Hepatology

Lahey Hospital and Medical Center

Sub-Investigators:

[name] MD

Advanced Endoscopy Fellow

Division of Gastroenterology and Hepatology

Lahey Hospital and Medical Center

Table of Contents

- **Research Objectives/Specific Aims/Outcomes Measures**
- **Background Information/Significance/Scientific Rationale**
- **Participant Selection/Eligibility**
- **Subject Enrollment**
- **Study Design/Procedures**
- **Study Calendar/Schematic/Schedule**
- **Potential Risks/Discomforts**
- **Potential Benefits**
- **Statistical Analysis**
- **Data Management**
- **Data and Safety Monitoring and Quality Assurance**
- **References**

Study Title: Comparison between angled-tip and straight-tip guidewire in biliary cannulation: A prospective, randomized trial

Protocol Version Number: Version 1.0 Protocol Date: 08/29/2022

Research Objectives/Specific Aims/Outcomes Measures

Wire-guided cannulation of the common bile duct is a standard technique utilized during Endoscopic Retrograde Cholangio-Pancreatography (ERCP) to ensure safe and effective access to the common bile duct via the ampulla of Vater. Due to the anatomy of the ampulla, and the orientation of the biliary orifice, a guidewire with an angled tip may allow easier and safer access to the common bile duct without inadvertent manipulation of the pancreatic duct. We aim to assess the technical and clinical outcomes between an angled-tip guidewire (GW) compared to a straight-tip guidewire in wire-guided cannulation of the common bile duct. We hypothesize that an angled-tip GW is associated with increased rate of successful cannulation, decreased procedure time and decreased rate of post-ERCP pancreatitis in wire-guided biliary cannulation during ERCP.

Primary Research Question:

Is the use of an angled-tip guidewire associated with increased rate of successful cannulation of the common bile duct in ERCP?

Secondary Research Questions:

Is the use of an angled-tip guidewire associated with decreased procedure duration?

Is the use of an angled-tip guidewire associated with reduced rates of post-ERCP pancreatitis?

Is cannulation more successful using an angled-tip wire in a particular type of papilla?

Background Information / Significance / Scientific Rationale

Endoscopic Retrograde Cholangio-pancreatography is a commonly performed procedure for diagnostic and therapeutic purposes in the setting of biliary tract pathology. During ERCP, bile duct access is performed with use of a catheter (sphincterotome) that is passed beyond the papilla into the bile duct. The utilization of a guidewire, over which the catheter is passed, to ensure selective common bile duct cannulation (as opposed to pancreatic duct cannulation) is associated with improved overall cannulation rates and lower risks of post-ERCP pancreatitis, and this practice has become standard.¹ A variety of guidewires are available to the endoscopist. The guidewires vary in size, stiffness and design of the tip of the wire, which may be straight, angled, J-shaped or tapered. Angled-tip guidewires were shown to result in decreased procedure duration, with a similar rate of cannulation and complications as compared to a straight tipped wire in a randomized-controlled trial including 239 patients.² Aside from this RCT, there is a paucity of literature that compares angled-tip and straight tip-guidewires in

Study Title: Comparison between angled-tip and straight-tip guidewire in biliary cannulation: A prospective, randomized trial

Protocol Version Number: Version 1.0 Protocol Date: 08/29/2022

biliary cannulation. In theory, an angled-tip guidewire may result in better technical performance including rate of successful cannulation, duration of procedure, and incidence of post-ERCP pancreatitis because of the anatomy of the ampulla of Vater and the oblique trajectory of the biliary orifice. Our goal is to compare the rate of successful cannulation, duration of procedure and incidence of post-ERCP pancreatitis between an angled-tip guidewire and straight-tip guidewire. This study will aid in the performance of ERCP and in the proper selection of devices to ensure safe and effective biliary cannulation. Additionally, this research may reduce healthcare expenditure by identifying an alternative device that may reduce the duration of the ERCP procedure.

Participant Selection / Eligibility

Patients undergoing ERCP with native papilla and pancreatobiliary disease who are candidates for ERCP with biliary cannulation are eligible for enrollment. Subjects must meet all inclusion criteria in order to be eligible to participate in the study.

Inclusion Criteria:

Patients undergoing ERCP for cholangiography, bile or tissue sampling from the gallbladder or bile duct, or for treatment of biliary diseases (removal of common bile duct stones, biliary stent placement)

Exclusion Criteria:

Patients who are less than 18 years old

Pregnant patients

Patients who have undergone previous bile duct cannulation or sphincterotomy

Patients who have undergone prior endoscopic balloon dilation or needle-knife fistulotomy

Patients who have undergone gastric surgery (Billroth gastrectomy II, Roux-en-Y gastric bypass)

Patients with acute pancreatitis

Patients who refuse endoscopic intervention

Patients with ampullary tumor, duodenal stenosis, or pre-operatively proven pancreaticobiliary malunion

Subjects will be recruited based upon their need to undergo ERCP for biliary diagnosis or therapy as determined by the principal investigator or sub-investigators. This determination will be made based upon the clinical requirement of endoscopic biliary cannulation. Subjects will be either inpatients or outpatients who require ERCP and bile duct cannulation. The overall sample size will be approximately 248 patients. Pregnant women will not be recruited for participation in this study as ERCP in certain pregnancies may be harmful to the fetus especially during the first trimester. Additionally, minors (age less than 18 years old) and prisoners will not be recruited or enrolled in the study, as these are vulnerable populations who may have a compromised ability to make an informed decision about participation.

Study Title: Comparison between angled-tip and straight-tip guidewire in biliary cannulation: A prospective, randomized trial

Protocol Version Number: Version 1.0 Protocol Date: 08/29/2022

Subject Enrollment

All patients enrolled in the study will be required to sign an informed consent form to participate in the study as well as for the resultant data to be collected and used for analysis and eventual publication. Consent will be obtained via a paper consent form on the day of procedure by the research team. A copy of the consent form will be made and given to the subject and the original copy will be stored in a secure file on site. All known risks, benefits and alternative therapies will be explained to the patient by either the PI or sub-investigators prior to signing the consent form. The patient will be randomized to a study arm in a 1:1 fashion by a computer-generated random number list via the REDCap Electronic Data capture application after informed consent has been obtained and just prior to the start of the procedure by either the PI or the sub-investigators.

Study Design and Procedures

This is a prospective, randomized, unblinded trial performed at Lahey Hospital and Medical Center. All procedures will be performed by experienced advanced endoscopists with over 2000 career ERCP's and 350 ERCP's performed per year, (or by the advanced endoscopy fellow under supervision of the attending gastroenterologist). Enrolled patients will be randomly assigned by a computer-generated number list to 2 groups (group 1, angled-tip GW; group 2, straight-tip GW). All procedures will be performed using standard duodenoscope or Exalt duodenoscope (JF-260V; Olympus Medical Systems Corp, Tokyo, Japan). For the procedure, patients will receive either general anesthesia or monitored anesthesia care as clinically indicated. Medications will be administered by a licensed anesthesiologist or CRNA. All procedures will be performed via short-wire technique using a 0.025-inch, 260cm-long angled guidewire with 5-cm hydrophilic tip (Jagwire Revolution, Boston Scientific, Natick, MA) or a 0.025-inch, 260-cm long straight guidewire with a 5-cm hydrophilic tip. (Jagwire, Boston Scientific, Natick, MA) For cannulation, attending gastroenterologists will be allowed 5 minutes to cannulate (from first contact of ampulla) or 5 passes inadvertently into the pancreatic duct (whichever occurs first). If the procedure is performed by gastroenterology fellow, the fellow will be allowed 5 minutes from first contact with the ampulla or 5 passes into the pancreatic duct (whichever occurs first). If the pancreatic duct is cannulated, double guide-wire technique will be performed with the same wire (0.025-inch guidewire) for an additional 5 minutes. If cannulation remains unsuccessful, needle-knife technique will be performed with pancreatic duct stenting performed. This protocol is similar to Vihervaara et al.² Post-procedurally, patients will be monitored for post-ERCP pancreatitis with either inpatient follow-up or via a phone call if procedure performed as outpatient. Post-ERCP pancreatitis will be defined as new or worsened abdominal pain combined with >3 times the normal value of lipase more than 24 hours after ERCP and requirement of hospital admission or prolongation of a planned admission. Routine blood work will be collected upon admission and during hospitalization as clinically warranted. Data will be collected using the REDCap data collection application and will be securely stored on LHMC secured servers.

Study Title: Comparison between angled-tip and straight-tip guidewire in biliary cannulation: A prospective, randomized trial

Protocol Version Number: Version 1.0 Protocol Date: 08/29/2022

Standard of Care: Procedure in both treatment groups is considered standard of care as they use FDA approved devices. Here at Lahey, The endoscopists use both guidewires. The guidewire is selected based on physician preference. While they typically start with a straight-tip wire, they would also use angled-tip guidewire if the straight tip guidewire does not achieve cannulation of the bile duct. Data shows that both guidewires are safe to use with similar rates of successful cannulation and adverse events.

Study Calendar / Schematic / Schedule

The main study-required visit will be the day of the planned procedure (ERCP). On this visit, the pre-procedural process will include a discussion with the patient regarding the risks and benefits of the procedure as well as a description of the study and consent for participation in the study. Pre-procedure data will be collected and entered into the data capture tool. The data collected will include patient demographics and indication for procedure. Randomization will then be performed immediately prior to the start of the planned procedure and the randomization assignment will be entered into the data capture tool. Data will then be collected immediately after the procedure and will include procedure duration, successful cannulation determination, pancreatic duct cannulation determination, types of guidewires used during procedure, fellows involvement in procedure and complications of procedure. On post-procedure day one to post procedure day five, post-procedural data will be collected by either inpatient assessment or by a telephone call to the subject if the procedure was performed on an outpatient basis by either the PI or sub-investigators. If there is a concern for possible post-ERCP pancreatitis, a lipase level will be checked on an inpatient or outpatient basis. There will be no other planned study-required visits after post-procedure day five. Subjects will be removed from enrollment if they choose to withdraw from the study.

Potential Risks and Discomforts

The main risk of participation in this study is breach of confidentiality that pertains to data collection. This risk will be addressed in the “data management” section. There will be no additional risk to subjects based upon randomization to either arm of the study as data has shown that either wire (angled-tip vs straight-tip) are equally safe and confer no higher risk of adverse events.²

The risk associated with ERCP includes bleeding, infection, perforation or post-ERCP pancreatitis.³ The risk of bleeding is 1.3%.³ The risk of infection (ascending cholangitis) is less than 1%.³ The risk of perforation is 0.1 to 0.6%.³ The risk of post-ERCP pancreatitis is 3.5%.³ These risks can range from mild in severity to severe and life threatening. These risks will be minimized by virtue of the procedures being performed by or under the supervision of experienced endoscopists with over 2000 procedures performed and by following evidence-

Study Title: Comparison between angled-tip and straight-tip guidewire in biliary cannulation: A prospective, randomized trial
Protocol Version Number: Version 1.0 Protocol Date: 08/29/2022

based practice in the pre, intra, and post-procedural care of the subjects. Adverse events will be reported to the appropriate Lahey Hospital and Medical Center committee and to the IRB.

Potential Benefits

Aside from the benefit from the procedure itself for therapeutic and diagnostic purposes, patients will not directly benefit from the research being performed. We hope that our findings will have benefits for future patients undergoing the ERCP procedure.

Statistical Analysis

The sample size needed to achieve statistical significance for the primary outcome is 248 (207 *1.2) after adding 20% screen failure rate. The power of the study to detect if there is a true difference will be 0.80. It will take approximately six months to reach the target accrual. The variables that need to be collected include demographics, co-morbidities, laboratory values, date of procedure, diagnosis, outcome of procedure (success of cannulation), duration of procedure, post-procedure complications (including post-ERCP pancreatitis) and fellow involvement in procedure. The outcome variables include rate of successful cannulation, and incidence of post-ERCP pancreatitis. Predictor variables include co-morbidities, indication for procedure and fellow involvement in procedure. Potential confounding variables include differing anatomy of papilla amongst subjects, underlying etiology of biliary obstruction (which may be different from suspected pre-procedure diagnosis) or unforeseen biliary pathology which alters procedure. The study endpoints will be achieved by showing a statistically significant difference in the rate of successful cannulation using an angled-wire as compared to a straight wire as defined as a p-value of less than 0.05. The proportion of procedures that are successful in the two treatment arms will be compared using chi squared analysis. Similarly, the rate of development of pancreatitis will be compared using chi squared analysis. The total duration of the procedure will be compared using a T-Test for comparing mean if the data are normally distributed or a Wilcoxon rank sum test if not normally distributed.

Data Management

All data will be collected using the REDCap Data Collection application and will be stored electronically on this platform. Only the PI and sub-investigators will have access to the password encrypted REDCap database. There will be no transmission of the acquired data off site. The data set will not include patient names or other identifiers. Information for this study will be available as required to the FDA, Massachusetts Department of Health, and LHMC IRB. Names of subjects will not be mentioned in publications or case reports.

Study Title: Comparison between angled-tip and straight-tip guidewire in biliary cannulation: A prospective, randomized trial
Protocol Version Number: Version 1.0 Protocol Date: 08/29/2022

Data and Safety Monitoring and Quality Assurance

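### Outpatient pancreatitis outcomes can rest on one unblinded call on an unfixed day from 1 to 5, so cases arising after an early call can be missed on a secondary outcome with about seven to nine expected events

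*Combined protocol and SAP*

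**What the plan says.** The Study Design and Procedures section defines post-ERCP pancreatitis as new or worse abdominal pain together with ">3 times the normal value of lipase more than 24 hours after ERCP and requirement of hospital admission or prolongation of a planned admission". It describes follow-up as inpatient for those in hospital and by a phone call, in the singular, for outpatients. Blood work is taken on admission and as clinically warranted during a stay.

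The Study Calendar section gives the timing: "On post-procedure day one to post procedure day five, post-procedural data will be collected by either inpatient assessment or by a telephone call". The PI or sub-investigators do this. It adds: "If there is a concern for possible post-ERCP pancreatitis, a lipase level will be checked on an inpatient or outpatient basis". It states no criterion for concern and no time for the test, and it plans no study visit after day five.

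The trial is declared unblinded, and no masked assessor or adjudication is described. Under Subject Enrollment, the PI or sub-investigators also carry out the randomization.

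Under Statistical Analysis: "Similarly, the rate of development of pancreatitis will be compared using chi squared analysis". No power is stated for this outcome. The only pancreatitis rate given is in Potential Risks and Discomforts: "The risk of post-ERCP pancreatitis is 3.5" per cent.

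**The concern.** Three features combine.

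- **Timing.** The contact day is open from 1 to 5, while part of the definition can be satisfied only more than 24 hours after the procedure. If the one outpatient call falls early, the plan describes no route by which later pain, testing or admission reaches the dataset.
- **Lipase.** The check is untimed. Under the wording of the definition, a raised value taken within 24 hours and not followed by another does not count.
- **Masking.** The people who gather the outcome know the allocation or have access to it, and the stated hypothesis is fewer cases with the angled wire. Whether a symptom raises concern is their judgement.

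The result is a likely under-count whose size depends on call day, and a possible difference in case finding between arms. Pancreatitis is part of the study hypothesis and one of the secondary research questions, and few events are expected, so small losses carry weight.

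**Working it through.** **Inputs**

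- Patients: 207 before inflation, 248 after (Statistical Analysis); overall size about 248 (Participant Selection).
- Allocation 1:1 (Subject Enrollment).
- Pancreatitis risk 3.5% (Potential Risks and Discomforts). This is a general ERCP figure, not a planning rate for these native-papilla patients.
- Significance level 0.05, stated for cannulation; two-sided is my assumption.

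**The plan's own figure.** 207 × 1.2 = 248.4, which matches the stated 248. The 207 itself cannot be rebuilt, because no cannulation rates are given. There is no stated event count for pancreatitis to reproduce.

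**Expected events = N × 0.035**

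| N | Total | Per arm | Central 95% binomial range of total |
|---|---|---|---|
| 207 | 7.2 | 3.6 | 3 to 13 |
| 248 | 8.7 | 4.3 | 4 to 15 |

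If the true rate were 5% to 10% in both arms (my range), 207 patients would give about 10 to 21 events.

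**Can a compliant contact miss a case?** Take an outpatient called on day one. The call is within the window. If the procedure was late the day before, 24 hours may not have passed, so no lipase value could yet qualify. Even after 24 hours, pain or admission may begin after the call. The protocol requires no second call. Such a case enters the data only if it reaches the investigators by some other path.

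**How precise is the comparison?** Take 4 events in each arm of 104 and 103 and use the Newcombe interval.

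- Proportions: 4/104 = 3.85% and 4/103 = 3.88%; difference −0.04 points.
- Wilson limits: 1.51% to 9.47% and 1.52% to 9.56%.
- Lower limit: −0.04 − √[(3.85 − 1.51)² + (9.56 − 3.88)²] = −6.2 points.
- Upper limit: −0.04 + √[(9.47 − 3.85)² + (3.88 − 1.52)²] = +6.1 points.

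An even split therefore leaves differences larger than the quoted 3.5% risk compatible with the data.

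**Power.** For an assumed halving, 3.5% to 1.75%, exact power of the uncorrected chi-squared test is 11% with 207 patients and 12% with 248. About 2,620 patients would be needed for 80%.

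**Effect of one case, arms of 104 and 103, uncorrected chi-squared**

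| Events | p | With one case fewer | p |
|---|---|---|---|
| 4 v 0 | 0.044 | 3 v 0 | 0.083 |
| 7 v 1 | 0.032 | 6 v 1 | 0.056 |

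These tables were chosen at the significance boundary. They show that one case can matter, not that it usually does.

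**The case against.** The case for the plan has real force, and most of it narrows the point.

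- **Number of contacts.** A reader might infer that every patient gets exactly one contact. The text does not say so. The singular wording makes one call the likely reading for outpatients only; the day 1 to 5 phrase could mean follow-up across the window, and inpatients are observed throughout their stay.
- **Definition.** A case needs pain and admission or a longer stay. A symptom-triggered lipase check fits that definition, and most true cases would surface as hospitalisations. This limits the loss. It does not recover an admission after an early call, possibly at another hospital.
- **Bias by arm.** The schedule is the same in both arms, and the documents do not say that the caller performed that patient's procedure. Differential ascertainment is a possibility arising from open-label conduct, not a built-in feature.
- **Chi-squared test.** Expected counts below 5 might suggest that the test is invalid. The calculation does not bear this out: at 3.5% in both arms of 104 and 103, the uncorrected test has a type I error of 4.7%. An exact unconditional (Boschloo) test would not remove the sensitivity to one case either (0.036 at 7 v 1, 0.069 at 6 v 1). Fisher's result for 7 v 1 depends on which arm has the seven: 0.065 in the arm of 104, 0.035 in the arm of 103. Replacing the test would be a preference.
- **Moving the call.** Shifting the outpatient call to day five looks like the obvious remedy. But it is the only outpatient monitoring contact described, so moving it would alter patient monitoring.

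**Conclusion.** The point holds as a cheap improvement. For outpatients, the plan as written allows the pancreatitis outcome to be closed before a qualifying case can arise, and it leaves the trigger for testing to unblinded judgement. Cases can be missed, and ascertainment could differ by arm; the pain and admission requirement reduces this risk without removing it.

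The size rests on the general 3.5% risk: about 7 events if 207 are analysed, about 9 if all 248 are. How many cases would be missed cannot be estimated, since the documents give neither the distribution of call days nor the outpatient share. The conclusion assumes that the singular call means what it appears to mean; if several calls are intended, the gap is one of wording, and the protocol should state them.

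A reader might go further and conclude that the trial's main result is at risk. It is not. Pancreatitis is a secondary question, and the Statistical Analysis section ties achievement of the endpoints to cannulation alone. What the trial cannot do is support a claim of reduced or equal pancreatitis risk from a p-value on so few events.

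**What to change.** 1. Leave clinical monitoring and any early call as they are. Add one fixed research time point at the end of the existing day 1 to 5 window, the same for every patient in both arms. Use one script covering pain, lipase tests with their times, and admission or prolonged stay since the procedure, including at other hospitals.
2. Have each possible event classified against the definition from an extract with the arm and the guidewire fields removed, by a team member not involved in that procedure. Only the PI and sub-investigators have REDCap access and they also randomize, so the extract has to be prepared deliberately; masking in so small a team will be imperfect.
3. Reconcile the 24-hour lipase element of the definition in Study Design and Procedures with the untimed lipase check in Study Calendar.
4. Beside the planned chi-squared test, report the risk difference with a Newcombe or Miettinen-Nurminen 95% confidence interval. State that neither reduced nor equal risk will be claimed unless the interval supports it.

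The cost is at most one short extra call for some outpatients, slightly more reliance on recall, a few minutes of masked classification per possible event, and a line or two in the analysis section. No visits are added and the sample size does not change.

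### Post-ERCP pancreatitis, a secondary outcome, is ascertained by unblinded investigators using an undefined trigger for lipase, so detection can differ by arm

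*Combined protocol and SAP*

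**What the plan says.** Study Design and Procedures: "This is a prospective, randomized, unblinded trial". No masking of patient, follow-up caller or outcome assessor is described anywhere. During the procedure "patients will receive either general anesthesia or monitored anesthesia care as clinically indicated".

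Subject Enrollment: randomisation is done "just prior to the start of the procedure by either the PI or the sub-investigators". Those roles therefore know the arm.

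Study Calendar / Schematic / Schedule: data for days one to five come from inpatient assessment or "by a telephone call to the subject if the procedure was performed on an outpatient basis by either the PI or sub-investigators". The next sentence sets the trigger for testing: "If there is a concern for possible post-ERCP pancreatitis, a lipase level will be checked on an inpatient or outpatient basis". No symptom threshold, script or scheduled lipase for all patients is given.

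Study Design and Procedures gives the case definition, which has three required parts:
- pain: "Post-ERCP pancreatitis will be defined as new or worsened abdominal pain";
- lipase above three times normal, more than 24 hours after ERCP;
- a need for admission, or a planned admission that is prolonged.

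The same section provides for routine blood work on admission and, as clinically warranted, during the stay. It does not say that lipase is part of it.

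The pre-procedure data named in the Study Calendar are demographics and indication. Statistical Analysis adds co-morbidities, laboratory values and other variables, but no pain score. It assigns pancreatitis a chi-squared comparison. The study endpoint itself is defined on cannulation success.

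**The concern.** A patient with no lipase result cannot meet the case definition and so counts as event-free. Outside admission blood work, whether a lipase is drawn depends on an undefined judgement. The natural reading is that this judgement belongs to the people collecting follow-up, who may know the arm and whose stated hypothesis is that the angled tip lowers pancreatitis. The entry symptom is the patient's own report, and the plan does not provide for keeping the wire unknown to the patient. The word 'worsened' has no listed baseline score to refer to.

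If probing or testing differed by arm, a difference in pancreatitis could appear with no true wire effect, or a real one could be hidden. The data set would not reveal it, because cases that were never tested leave no trace and cannot be recovered by analysis. Operators cannot be blinded to the wire, but the patient's knowledge and the test trigger can be controlled.

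**Working it through.** The plan gives no figure for pancreatitis ascertainment, so there is none to reproduce. The stated sample size is 207 × 1.2 = 248.4, given as 248. The point does not depend on it.

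**Inputs from the protocol.** Pancreatitis risk 3.5% (Potential Risks and Discomforts). 207 patients before inflation, chi-squared test, p < 0.05 (Statistical Analysis). 1:1 allocation (Subject Enrollment), hence arms of 103 and 104.

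**Assumptions.** Two-sided test without continuity correction; the plan states neither. The 0.05 level is stated for the primary outcome and is applied here to pancreatitis. True risk is equal in both arms. Detection is complete in one arm and a fraction s in the other; the documents give no value for s, so a range is shown.

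**Expected cases.** 0.035 × 103 = 3.6 and 0.035 × 104 = 3.6; in total 0.035 × 207 = 7.2. One missed case is roughly a quarter of an arm's count (1/3.6 = 0.28).

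**Apparent risk ratio.** (0.035 × s) / 0.035 = s.

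**False rejection.** This is the sum, over all pairs of counts (i, j), of P(i | 103, 0.035) × P(j | 104, 0.035s) for pairs where the uncorrected chi-squared gives p < 0.05. Binomial probabilities are used, with reduced detection in the arm of 104.

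| Detection s | Observed risks | Apparent risk ratio | False rejection |
|---|---|---|---|
| 100% | 3.5% v 3.5% | 1.00 | 4.7% |
| 90% | 3.5% v 3.15% | 0.90 | 4.9% |
| 70% | 3.5% v 2.45% | 0.70 | 6.7% |
| 50% | 3.5% v 1.75% | 0.50 | 11.0% |

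If all 248 were randomised (124 per arm, 0.035 × 124 = 4.3 cases each), 90% and 50% detection give 4.6% and 12.0%, against 4.3% with equal detection.

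**How far a single case can move the p-value.** With 0 of 104 v 4 of 103, the uncorrected chi-squared gives p = 0.042; with 1 v 4 it gives p = 0.17. For 0 v 4, the continuity-corrected test gives 0.13 and Fisher's exact test 0.06 (0.12 with 103 per arm). At equal 3.5% risks the probability of that exact split is 0.965^104 × P(4 of 103) = 0.0246 × 0.195 = 0.005.

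**The case against.** The strongest reply is that the definition also requires admission or a prolonged stay. An outpatient with pain who is never tested and never admitted could not be a case whatever the lipase, and a patient ill enough to be admitted is the least likely to go untested. Admission blood work may include lipase. The lipase threshold is objective and limits false positives. This narrows the route by which cases are lost but does not close it: the plan does not say that admission blood work includes lipase, a threshold cannot recover untested cases, and admission is itself decided without masking.

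A reader might infer that one unordered lipase can decide the pancreatitis result. The documents do not support that. It needs a 0 v 4 split, which is improbable and significant only by the uncorrected test, and the plan does not say whether a correction applies. The missed patient would also have to meet the admission criterion. Much of that fragility comes from expecting only about seven events, which is a separate matter.

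A reader might also infer that the plan shows bias in favour of the angled tip. It shows neither direction nor size. Three links are readings of the text rather than statements in it: that the data collectors judge concern, that patients may learn which wire was used, and that no baseline pain is recorded (the variable lists are introduced as inclusive and inpatients have charts).

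Finally, a separate masked caller might seem essential. Data Management restricts REDCap access to the PI and sub-investigators, so requiring one could mean extra staff and changed access.

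**Conclusion.** The concern holds in limited form. As written, the plan allows detection of a secondary outcome to depend on knowledge of the arm, through an undefined test trigger and an unmasked admission decision. The estimate is more exposed than the test. Under the assumed detection of 90% to 50% in one arm, the apparent risk ratio moves one-for-one from 0.90 to 0.50, while false rejection rises only from 4.7% to between 4.9% and 11.0%. These sizes rest on the protocol's 3.5% risk, on detection fractions the documents do not supply, and on an uncorrected two-sided test. The bias is possible, not demonstrated. The primary cannulation comparison is untouched and no change in sample size follows. The point is worth acting on because the remedy is cheap and must be in place before follow-up starts.

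**What to change.** 1. Do not tell patients which wire was used until their last study contact. Anesthesia or monitored anesthesia care during the procedure makes this practical.
2. Ask every patient in both arms the same scripted abdominal-pain question. Tie the lipase drawn for outcome ascertainment to the plan's own pain criterion in place of an undefined concern. This governs outcome measurement only and leaves clinical care unchanged.
3. Record a pain score before randomisation, so that worsening has a reference.
4. Where a sub-investigator who was not in the room is available, have that person do follow-up with the arm hidden on the form. Do not add staff for this.

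The cost is a short script, one baseline field and a few more lipase tests. The admission decision stays unmasked under all four steps, and the report should state this as a limitation.
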